### 4. Research Design and Methods

This study will evaluate the feasibility and acceptability of active video game-based physical

activity intervention among BC survivors within the support group setting. In addition, we will also compare the changes in physical activity among participants who were in the active video game-based physical activity intervention support group to those who were in the existing the UTMB breast cancer support group. Participants (N=60) will be randomized to participate in the support group that uses the active video game-based physical activity intervention (intervention group) or in the existing UTMB breast cancer support group with pedometers (control group) for 12 weeks. The home-based self-paced portion of the intervention will mainly be delivered through the participant manual. In the fourth cohort, BC survivors (N=20, aged 55 to 79 due to the aging grant restrictions) will be recruited and randomly assigned to intervention or control condition for a 12-week period. The intervention group will participate in weekly active video game web-based group sessions. The control group will receive weekly conference calls plus wearable tracker to track their physical activity for 12 weeks.

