A recruitment letter will be mailed to contact potential participants in the cancer or volunteer registries. We will also collaborate with local cancer support groups. Newspaper advertisement and flyers will also be used as additional recruitment tools. We will recruit participants in three cohorts. First and second cohort will consist of 10 people, 5 in the intervention group and 5 in the control group. The third cohort will consist of 40 people, 20 in the intervention group and 20 in the control group. In order to randomize a total of 60 participants, we will need to recruit up to 80 individuals due to drop-outs between screening and randomization. The fourth cohort will consist of 20 people (age 55 and 79 to grant

restrictions), 10 in the intervention group and 10 in the control group. In order to randomize a total of 20 participants, we will need to recruit an additional 80 individuals to account for potential drop-outs between screening and randomization. A total of 160 individuals will be recruited for Cohort 1-4 in order to randomize a total of 80 participants. Screening script, recruitment letter, flyer, presentation blurb are presented in **Appendix A**.

4.3 Inclusion/Exclusion Criteria. Research staff will follow the screening script to determine eligibility when potential participants express interest in the study. Potential participants must meet all of the inclusion criteria in order to be eligible to participate in the study.

Primary inclusion criteria will include for Cohort 1-3:

- Provide informed consent
- Diagnosed with primary female breast cancer
- English-speaking between the ages of 18 years or older
- Able to read and write in English
- Obtained approval from oncologists for the participant to be involved in the physical activity based support group
- Able to travel to the UTMB sites (Victory Lakes or Galveston)
- Able to move arms and legs as well as ambulate
- Able to see TV screen from a distance of 2 to 4 feet

Primary inclusion criteria for Cohort 4 due to grant restrictions will include:

- Ability to provide informed consent
- Diagnosed with primary female breast cancer
- 55 years to 79
- Able to speak, read, and write in English
- Able to travel to UTMB locations and/or MD Anderson Victory Lakes
- Able to move arms and legs as well as ambulate
- Has a smartphone, tablet or computer and daily access to a reliable internet

Inclusion criteria for Cohort 4 due to pandemic (e.g., COVID-19) restrictions will include:

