- Ability to provide informed consent via telephone or through internet
- Diagnosed with primary female breast cancer
- 55 years to 79
- Able to speak, read, and write in English
- Able to move arms and legs as well as ambulate
- Has a smartphone, tablet or computer and daily access to a reliable internet

Potential participant meeting any of the exclusion criteria at screening will be excluded from study participation

Ineligibility criteria will include:

- Being pregnant
- Dementia
- Currently engage in  $\geq 150$  minutes of planned moderate physical activity per week for the prior week

- Are involved in another physical activity intervention

Ineligibility criteria for Cohort 4 will include all criteria listed above. However, cohort 4 has an addition of no access to an internet-connected smart device (smartphone, tablet, or computer) being an ineligibility criterion.

**4.3 Randomization Procedures.** Participant in cohorts 1 to 3 will be randomly assigned to be in the active video game-based physical activity intervention group (intervention group) or the existing UTMB Breast Cancer support group with pedometer (control group). Participant in cohort 4 will be randomly assigned to be in the weekly active video game web-based group sessions with wearable tracker (intervention group) or receive weekly conference calls plus wearable tracker (control group). We will randomize participants by using sequentially numbered opaque sealed envelopes for cohorts 1 to 4. The sequentially number will be the Study ID #1 to #80 for cohort 1-3. A project staff who is not involved in the assessment will use the random number generator (<https://www.randomizer.org/>) to assign each study ID number to either intervention group or control group. The project staff who is not involved in the assessment will write the group assignments will be written on pieces of paper, placed under a piece of carbon paper, wrapped in aluminum foil, and then sealed one per opaque envelope. The same procedure will be used for cohort 4.

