**4.4 Intervention Group Procedure.** The primary purpose of this study is to investigate the feasibility and acceptability of active video game-based physical activity intervention among BC survivors within the support group setting (in person for cohorts 1-3 and over the web for cohort 4) with home-based components. Cohort 4 will have the addition of yellow and red theraputty and grip exercise to the 12-week intervention components. The 12-week intervention components are presented in Table 2. Cohort 4 will not receive a Wii Fit Fitness tracker and we will mainly use Xbox 360 video games but may use the Wii video games.

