By wearing the Fitbit, participants will be able to track individual and group daily steps on the Fitbit dashboard. Having the ability to see the weekly accomplishments will further enhance motivation for activity through social comparison and relatedness.

4.5 Control group procedure. Participants in cohort 1-3 that are randomized to the control group will be introduced to the current facilitator for the existing Breast Cancer Support Group at the UTMB Breast Health and Imaging Center after the initial assessment. Control group participant will be encouraged to participate in the Breast Cancer Support Group for the next 12-weeks on a monthly basis. Examples of topics covered in the Breast Cancer Support Group are presented in **Appendix D**. The support group follows the *Navigating Life’s road Map After Breast Cancer* curriculum from the Reconstruction of a Survivor (<http://www.reconstructasurvivor.org/index.html>) organization. Control group participant will also be provided a pedometer (Digi Walker or Omron Tri Axis HJ-

Figure 3. Digi-Walker or Omron Tri Axis HJ-321 Pedometer

321) to be worn for 12-weeks (Figure 3). Participants will have a choice to use either a Digi Walker or Omron Tri Axis pedometer. Participants in the control group will also receive the American Cancer Society's personal health manager kit as it is standard of practice at the UTMB Breast Health and Imaging Center. They will also be recording their activities on a daily, weekly, and monthly basis.

For the fourth cohort, weekly conference calls to check on participants' well-being and to provide survivorship information will be scheduled over the 13-week study period (Appendix B2d). Control group participants in the cohort 4 will be given a wearable tracker with charger to use during the study period. A list of local breast cancer/cancer support groups will also be given to the participants that is available on the UTMB website. MD Anderson personnel (e.g., [name]) will be involved in cohort 4 control group activities.

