**Table 3a. Summary of measures and evaluation schedule (pre-pandemic restrictions)**

Measures	Week 0	Week 1	Week 7	Week 14
Objective measures				
SPPB to measure physical function and Hand grip strength test		X	X(hand grip strength only)	X
Height, Weight, and Waist Circumference	X	X	X	X
Actigraph wGT3X GT monitors (Physical activity)—cohorts 1 and 2	X		X	X
Actigraph GT9X monitors (Physical activity)—cohorts 3 and 4	X		X	X
Participant self-report measures				
Demographics	X			X
Program satisfaction			X	X
CHAMPS to measure physical activity (cohorts 1, 2 and 4)	X			X
BRFSS physical activity questions (cohort 3)	X			X
Functional Assessment of Cancer Therapy (Quality of life)	X		X	X
PROMIS-Cancer Physical Function	X			X
PROMIS-Cancer Fatigue	X			X
Dietary screener/recall	X			X
Psychosocial variables related to exercise				
Exercise motivation	X		X	X
Psychological Feelings	X		X	X
Self-regulation	X		X	X
Social support	X		X	X
Task and Barrier Self-efficacy	X		X	X
Posttraumatic Growth Inventory-SF (cohort 3)	X		X	X

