The changes in physical activity level among breast cancer survivors who were randomized into the Pink Warrior intervention or into the existing UTMB breast cancer support group with pedometer will be evaluated at baseline and at week 14. Physical activity changes such as meeting the recommended 150 minutes per week or 7,000-10,000 steps/day will be measured by Actigraph wGT3X BT monitors. Wear time will be seven days at each assessment point. Because continuous measurement is not feasible, a week-long sample will be taken at baseline, week 7(+/- one week) and week 14(+/- one week). Physical activity estimates will only be considered as valid if the monitor is worn  $\geq 10$  hours per day on  $\geq 4$  days. Also through the community healthy activities model program for seniors (CHAMPS) self-reported questionnaire at baseline and at week 14 will be administered for participants in cohorts 1, 2, and 4. The changes in dietary pattern will be evaluated using the Dietary Screener Questionnaire used in the National Health and Nutrition Examination Survey 2009-10. The screener captures frequency of fruits, vegetables, dairy/calcium, added sugar, wholegrains/fiber, red meat, and processed meat consumption within the past 30 days. Health related quality of life outcomes will be measured by using the Functional Assessment of Cancer Therapy and Patient reported Outcomes Measurement information System (PROMIS) adapted testing.

For the third and fourth cohort we will measure physical activity changes (e.g., 150 minutes per week of activity or 7,000-10,000 steps/day) by using Actigraph GT9X to accommodate the increased number of participants in cohort three and four. Based on participant feedback from cohorts 1 and 2, we also removed the CHAMPS self-reported questionnaire for the third cohort to reduce participant burden. Instead, we are adding eight questions from the 2015 Behavioral Risk Factor Surveillance System (BRFSS) questionnaire to the main demographic questionnaire.

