**Aim 2: Compare the support group using the active video game-based physical activity intervention (intervention group) to the existing UTMB breast cancer support group with pedometer (control group for cohorts 1-3) or the telephone-based support group with the UTMB support group (control group for cohort 4).** We will use analysis of covariance (ANCOVA) to test the post-intervention differences at 12-weeks (physical activity) between the two groups, controlling for baseline and other covariates that are significantly different at baseline. Intent to treat analysis will be used to handle missing data. ANCOVA will also be used to evaluate the secondary outcomes (physical function and quality of life). We will explore the changes in psychosocial variables using linear mixed models to investigate differences between groups and over here time points. Since this is a pilot study and it is not powered to detect significant differences of small to moderate effects, we hypothesized that the intervention group will show an improvement in physical activity, physical function, and quality of life compared to the control group. We also hypothesize that the intervention group will show an improvement in self-reported scores on self-efficacy, self-regulation, intrinsic motivation

**Aim 3: Develop tools for implementation of the Pink Warrior intervention within the clinic and community settings.** Development of a trainer's manual for the intervention will mainly be based on descriptive analyses using the facilitator's weekly group log. The facilitators will indicate whether or not they were able to cover the entire session as planned and facilitator will also be asked to provide feedback regarding the facilitator's guide and their feedback regarding the group activities.

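### ANCOVA covariates beyond the baseline outcome are picked by baseline significance tests, so the adjustment set depends on chance; cohort is not named in the model and matters where cohorts are combined

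*Combined protocol and SAP*

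**What the plan says.** Section 7.0, Aim 2, tests the post-intervention difference in physical activity by ANCOVA, "controlling for baseline and other covariates that are significantly different at baseline". ANCOVA is also named for physical function and quality of life. Only the baseline value is fixed in advance: the section gives no candidate covariates, no baseline test and no significance level, and does not mention cohort.

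Cohorts differ in these ways:

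- **Accelerometer.** Cohorts 1 and 2 use one Actigraph model. Section 4.6 measures the later cohorts "by using Actigraph GT9X to accommodate the increased number of participants in cohort three and four".
- **Intervention setting and tracker.** For cohort 4, section 4 states: "The intervention group will participate in weekly active video game web-based group sessions". Section 4.4 adds: "Cohort 4 will not receive a Wii Fit Fitness tracker and we will mainly use Xbox 360 video games".
- **Comparator.** Cohorts 1-3 use the existing support group with pedometer. Section 4.5 says: "For the fourth cohort, weekly conference calls to check on participants' well-being and to provide survivorship information will be scheduled".
- **Age.** Adults of 18 or older in cohorts 1-3; 55 to 79 in cohort 4 (section 4.3, inclusion criteria).

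On allocation, section 4.2 says: "First and second cohort will consist of 10 people, 5 in the intervention group and 5 in the control group". It plans 20 and 20 in cohort 3, and 10 and 10 in cohort 4. The randomisation section uses a random number generator "to assign each study ID number to either intervention group or control group" and mentions neither blocking nor stratification.

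Section 7.1 intends the pilot's effect sizes to inform larger trials, and gives cohort 4 (N=20) its own purpose of estimating Cohen's d.

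**The concern.** A covariate is worth adjusting for when it predicts the outcome. A baseline test in a randomised trial says nothing about that. It flags whichever variables happened to differ between arms and passes over a strong predictor that happened to balance. Two analysts with different candidate lists could follow this plan on the same data and report different effects. Since the estimates are meant to feed later sample-size work, the estimate itself is at stake more than any p-value.

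Cohort is the opposite case. It is a known design factor that may relate to the outcome, and equal splits ensure that a screening rule never picks it.

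**Working it through.** The plan gives no figure on this point to reproduce. The alpha of 0.05, the number of candidates and the simulation parameters below are assumptions.

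**1. Chance of at least one spurious covariate.** For k independent continuous candidates tested at 0.05, the chance is 1 - 0.95^k.

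- k=5: 1 - 0.95^5 = 0.226, or 23%.
- k=10: 1 - 0.95^10 = 0.401, or 40%.

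Section 4.6 names six demographics, but gender is fixed by the female breast cancer criterion, which leaves at most five usable candidates. Four of these (race/ethnicity, education, diagnosis, treatment) are categorical. If they were binary and tested by Fisher's exact test, simulated false selection is about 1-2% each at N=20 and 2.5-3% at N=60. With age at 5%, the chance is 1 - 0.95 × (1 - f)^4:

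- N=20: 0.087 (f=0.01) to 0.124 (f=0.02).
- N=60: 0.141 (f=0.025) to 0.159 (f=0.03).

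So these demographics alone give about 9-16%. Adding continuous baseline measures would raise it.

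**2. Effect on the estimate.** The simulations assume no true effect, baseline-outcome correlation 0.6, 5 or 10 independent candidates, two of them prognostic with coefficient 0.3 each, and balanced arms. The table gives the variance of the rule's estimate divided by that of a prespecified model. That model contains the baseline value, cohort at N=60, and the named covariates.

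| Prespecified model names | N=60 (cohorts 1-3) | N=20 (cohort 4) |
|---|---|---|
| one prognostic covariate | about 1.05-1.10 | about 1.10-1.20 |
| no covariate | 0.94-0.97 | 1.02-1.11 |
| three, one of them prognostic | 0.98-1.05 | 0.90-1.04 |

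The third row also covers weaker prognostic coefficients. Against the one-covariate model, the two estimates from the same data differ on average by 0.06-0.07 SD at N=60 (95th percentile 0.18-0.19) and by 0.13-0.15 SD at N=20 (0.40-0.48). Bias is at most 0.006 SD. Type I error is 4.2-4.4% at N=60 and 4.5-4.8% at N=20.

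**3. Can the rule select cohort?** At planned splits of 5:5, 5:5, 20:20 and 10:10, observed counts equal expected counts in every cell. A chi-square test of cohort by arm is then exactly 0 and cohort is never selected. Under unrestricted allocation it enters only by chance (4.6% of simulated trials).

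**4. Cost of omitting cohort.**

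- *Cohorts 1-3.* An assumed accelerometer shift of 0.5-0.8 SD in cohort 3, equal at baseline and follow-up, changes the squared residual SD by a factor of 0.999-1.018. A later trial sized on it would need about 0-2% more participants.
- *All four, only if pooled.* A cohort 4 shift of 0.5-0.8 SD at both times gives factors of 0.998-1.014 and type I error of 3.7-3.9%. A shift at follow-up only gives 1.062-1.180 and 2.7-3.4%.
- *Meaning of a pooled estimate.* Weights would be 60/80 = 0.75 and 20/80 = 0.25. Hypothetical effects of 0.5 SD (cohorts 1-3) and 0 (cohort 4) would be reported as 0.75 × 0.5 + 0.25 × 0 = 0.375 SD, which describes neither comparator.

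**The case against.** **Consequences are small.** The rule introduces no bias, and false positives are not inflated. Section 7.1 makes feasibility the primary purpose, and Aim 2 is declared unpowered for small to moderate effects. This stands and limits the severity. It does not remove the point, because the declared use of Aim 2 is estimation.

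**The precision loss depends on the benchmark.** This also stands. The 10-20% at N=20 requires naming exactly one truly prognostic covariate with a coefficient of 0.3, which no section supports. A list of mostly weak covariates can do as badly as the rule, or worse. The case for prespecification therefore rests mainly on removing chance selection, and the list must be very short.

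**Pooling.** A reader might infer that all four cohorts go into one model that ignores the change of comparator. The documents do not support that reading. Section 7.0 opens by mentioning analyses of cohorts 1-4, but Aim 2 lists the two controls as alternatives, and section 7.1 justifies 60 and 20 separately, which points towards separate analysis. Without pooling, the comparator, tracker, setting and age differences do not enter any one model, and only the accelerometer change remains within cohorts 1-3.

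**A cohort term has limits.** It cannot reconcile different instruments. Under section 4.6, physical function is measured by the SPPB in cohorts 1 and 2 and later by the Senior Fitness Test with two SPPB subsections; Table 4 moves cohort 4 to a reduced set by video.

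**Conclusion.** The concern holds as a minor point. The selection rule is explicit, depends on chance and ignores prognosis. Under an assumed alpha of 0.05, a spurious covariate enters in 23% (5 candidates) to 40% (10) of trials with independent continuous candidates, and less often with correlated or exactly tested categorical ones. The main harm is an effect estimate that depends on chance selection, most visibly in cohort 4, where it is the declared product of 20 participants. The variance figures are simulation results that depend on the benchmark, not properties of this trial.

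A reader might infer that the rule biases the comparison or makes it anticonservative. It does neither: in the simulations the test is at or slightly below nominal, and clearly conservative (2.7-3.4%) only if all cohorts are pooled and a large cohort 4 shift appears at follow-up alone.

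The omission of cohort is certain as a matter of text. Its effect is small within cohorts 1-3 and conditional on pooling beyond that.

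**What to change.** Replace the covariate clause in Aim 2 with:

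> Each ANCOVA adjusts for the baseline value of the outcome, for cohort where cohorts are combined, and for at most one or two strongly prognostic covariates named in advance (none or one in cohort 4 alone); no covariate is chosen by a baseline significance test.

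In addition:

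- State whether cohorts are pooled and whether allocation was balanced within cohort.
- Report the arm difference separately for cohorts 1-3 and cohort 4. The comparators differ, and a cohort main effect does not separate the two contrasts.
- Combine cohorts for physical function only on components measured in the same way.
- Keep baseline tables descriptive.

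**Cost.** Only wording changes; no new data are needed. Cohort uses 3 residual degrees of freedom if all four are pooled, 2 in cohorts 1-3 and none in cohort 4 alone; each named covariate uses one more. In cohort 4 the model with arm and baseline leaves 20 - 3 = 17, hence the limit on the list. Separate estimates are less precise: simulated 95% half-widths are about 0.39 SD (cohorts 1-3) and 0.74 SD (cohort 4), against 0.33 SD pooled.

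### Intention to treat is given as the missing-data method, but it supplies no missing value; the single-time-point ANCOVA has no rule for absent week-14 accelerometry and leaves the scheduled week-7 recording unused

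*Combined protocol and SAP*

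**What the plan says.** Section 7.0, Aim 2, states the primary analysis: "We will use analysis of covariance (ANCOVA) to test the post-intervention differences at 12-weeks (physical activity) between the two groups", adjusted for baseline and for covariates that differ at baseline. On missing data it says only: "Intent to treat analysis will be used to handle missing data". It continues: "ANCOVA will also be used to evaluate the secondary outcomes (physical function and quality of life"). Psychosocial variables alone are to be explored "using linear mixed models to investigate differences between groups". No imputation method, missingness assumption or sensitivity analysis appears anywhere.

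Section 4.6 (text after Table 3b) schedules the accelerometry: "a week-long sample will be taken at baseline, week 7(+/- one week) and week 14(+/- one week"). Tables 3a and 3b show it at weeks 0, 7 and 14 for all cohorts. The same section says that activity change in the intervention group and the control group "with pedometer will be evaluated at baseline and at week 14".

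Four provisions bear on whether a final value will exist:

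- Section 4.6: "Physical activity estimates will only be considered as valid if the monitor is worn" for at least 10 hours a day on at least 4 days.
- Section 4.7: a repeat week of wear is offered at Assessment 1, before randomisation. No repeat is described for week 7 or week 14.
- Sections 6.0 and 6.1: participation ends after a serious adverse event, for certain medical reasons, or on withdrawal of consent. The contact described afterwards is a safety call or a request for equipment; outcome collection is not mentioned.
- Section 4.2: the recruitment allowance covers losses before randomisation only.

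**The concern.** Intention to treat answers which participants count and under which arm. It cannot answer what number stands in for a week-14 value that was never recorded. An ANCOVA on one final value needs that number. Without a rule, the analyst either omits the participant, which sits badly with the stated intention, or chooses a fill-in after seeing the data.

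The wear-time rule means that even people who attend week 14 can lack a valid outcome. If the people lost are the less active ones, and this differs between arms in rate or mechanism, the complete-case comparison is distorted. Week-7 activity, which could correct part of this, is already being collected.

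At stake is the Aim 2 estimate for physical activity, the primary outcome of that aim. Section 7.1 intends to use the pilot's findings to set effect sizes and sample sizes for larger trials.

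**Working it through.** **Is there a figure to reproduce?** No. The documents give no post-randomisation loss rate, no SD and no correlation between visits. The sample size of 60 in section 7.1 is not at issue here, and it cannot be rebuilt because SD, alpha and power are not stated. Every simulation input below except the arm size is therefore an assumption.

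**Inputs**

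- 30 per arm: cohorts 1–3 in section 4.2 (5 + 5 + 20).
- Assumed: activity in SD units; correlation of baseline with weeks 7 and 14 of 0.6, and of week 7 with week 14 of 0.7; no true effect.
- Assumed loss in a selective arm: logit Pr(week 14 missing) = α − 1.5 × (week-7 activity in SD), with α set to give the stated rate. Loss in a non-selective arm is random.
- 10,000 runs per scenario; Monte Carlo error at most 0.003 SD.

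**Estimators**

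- Complete case: regress Y14 on arm and Y0 among those with Y14; take the arm coefficient.
- Week-7 model: τ14 = δ + γ·τ7. Here τ7 is the arm coefficient for Y7 given Y0 in everyone with week 7, and δ and γ are the coefficients of arm and Y7 for Y14 given Y0 and Y7 in those with Y14. On 60 simulated data sets this matched an unstructured repeated-measures mixed model to within 2 × 10⁻⁸.

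**Bias in SD units**

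| Scenario (no true effect) | Loss, intervention vs control | Complete case | Week-7 model |
|---|---|---|---|
| Intervention arm selective | 20% vs 10% | +0.078 | −0.001 |
| Intervention arm selective | 30% vs 10% | +0.116 | +0.002 |
| Both arms selective, unequal rates | 20% vs 10% | +0.038 | +0.001 |
| Both arms selective, unequal rates | 30% vs 10% | +0.078 | +0.003 |
| Low loss, intervention arm selective | 10% vs 5% | +0.045 | +0.002 |
| Low loss, intervention arm selective | 5% vs 5% | +0.019 | −0.003 |
| Same mechanism and rate in both arms | 10–30% in each | within 0.003 | within 0.003 |
| Intervention arm selective, half of those lost lack week 7 | 20%, 30% vs 10% | +0.078, +0.117 | +0.035, +0.049 |
| Intervention arm selective, all of those lost lack week 7 | 20%, 30% vs 10% | +0.078, +0.113 | +0.078, +0.113 |
| Loss follows week-14 activity, intervention arm | 20%, 30% vs 10% | +0.150, +0.217 | +0.110, +0.159 |

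**In steps.** At an assumed SD of 2000 steps/day the first two rows are 0.078 × 2000 = 156 and 0.116 × 2000 = 232. At an SD of 4000 they are 312 and 464. Section 7.1 speaks of 1000 to 2000 steps.

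**Against sampling error.** The SD of the estimate in the first two rows is 0.224 and 0.234 for complete case, and 0.223 and 0.231 for the week-7 model. Precision is therefore almost unchanged. The 95% half-width of one pilot is about 1.96 × 0.23 = 0.45 SD. Root-mean-square error, √(bias² + SD²):

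- 20% vs 10%: √(0.078² + 0.224²) = 0.237, against 0.223, a fall of about 6%.
- 30% vs 10%: √(0.116² + 0.234²) = 0.261, against 0.231, a fall of about 12%.

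**The case against.** The strongest reply is that this is a feasibility pilot. Sections 4.4 and 7.1 say so, and section 7.0 says it is not powered for small to moderate effects. A bias of about 0.1 SD is lost in a half-width of about 0.45 SD. The plan also works to limit loss: section 4.6 provides reminders, section 4.7 provides contacts to arrange monitor drop-off before week 14, and section 8.1 expects most participants to comply. Leaving out week 7 may be deliberate, since section 4.6 evaluates activity change at baseline and week 14. All of this stands, and it sets the severity. It does not supply a rule for a missing value, and a confidence interval shows sampling error, not bias.

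Four stronger readings are tempting, and the documents do not support them.

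- A reader might infer that the plan would carry the last value forward, so that the error could run in either direction. No carry-forward rule is mentioned anywhere.
- A reader might infer that the later trial will be sized wrongly. That would need a loss rate and a loss mechanism, and the documents give neither.
- A reader might take section 6.0 to forbid outcome collection after discontinuation. It is silent on this.
- A reader might take the 12-week wording in section 7.0 for a second endpoint. Set against the week-14 schedule, it is a mismatch of labels.

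**Conclusion.** The point holds in a limited form. The sentence on missing data cannot be carried out as written for an ANCOVA on one final value, and nothing elsewhere fills the gap. Scheduled week-7 accelerometry that could reduce the resulting bias is not used.

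The likely size is +0.08 to +0.12 SD at 20–30% against 10% loss, and about +0.02 to +0.045 SD at 5–10% loss, when loss in the intervention arm follows week-7 activity. Using week 7 brings this to about 0. There is no gain if everyone lost also lacks week 7, or if both arms share one loss mechanism and there is no true effect. The gain is only partial if loss follows week-14 activity itself.

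The bias is below one pilot's sampling error and rests wholly on assumed correlations and loss rates. It concerns Aim 2 and the effect sizes to be passed on, not feasibility. This is a cheap improvement of lower severity.

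**What to change.** In section 7.0, Aim 2, replace the intent-to-treat sentence and the physical-activity ANCOVA with wording such as this, and limit the secondary-outcome ANCOVA sentence to match:

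> Participants are analysed in the arm to which they were randomised. Accelerometer activity is analysed with a mixed model for repeated measures on weeks 7 and 14, with baseline, baseline-by-visit, arm, visit and arm-by-visit; the primary contrast is at week 14. All participants with a valid week-7 or week-14 value contribute; those with neither are counted and reported by arm with reasons. The same model is used for the Functional Assessment of Cancer Therapy. Secondary outcomes without a week-7 value in all cohorts keep baseline-adjusted ANCOVA in participants with a final value, and are described as such. A sensitivity analysis shifts imputed missing week-14 values in the intervention arm over a range fixed before the data are seen (for example 0 to −0.5 SD).

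Tables 3a and 3b both schedule "Functional Assessment of Cancer Therapy (Quality of life") at week 7, so the model applies to it in every cohort. Multiple imputation using week 7 would serve equally well.

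Two clarifications go with this. Align the 12-week wording in section 7.0 with week 14. Reconcile section 6.0 with the intention-to-treat statement on whether outcomes are still collected from consenting participants who stop activities; this leaves the decision to stop as it is.

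The cost is SAP wording and slightly more analysis work, with no new visit or measurement. The mixed model assumes data are missing at random and brings almost no gain in precision. It does not remove bias from loss driven by week-14 activity, which is why the sensitivity analysis is included.
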